4.0 Treatment Assignment

- 4.1 All patients who meet the eligibility criteria, sign the patient informed consent form, obtain physician consent, and complete baseline assessments will immediately be randomized to one of four treatment arms. Randomization will be determined by means of a computer-generated random number table.
 - 4.1.1 This study will use a block-randomized scheme with block sizes of 8 to ensure an equal distribution among the four arms.
 - 4.1.2 A total enrollment of 72 patients is planned (18 in each treatment arm).
 - 4.1.3 Treatment sequence in the four trial arms will be as follows:

Treatment Arm	Condition
1	Calcitriol 45 µg : Patients will be given 45 µg/week of calcitriol beginning at baseline for a period of 12 weeks.
2	Home-Based Exercise : Patients will be given a progressive walking and resistance band exercise treatment and a daily multivitamin for a period of 12 weeks.
3	Calcitriol 45 µg and Home-Based Exercise : Patients will be given 45 µg/week of calcitriol along with a progressive walking and resistance band exercise treatment for a period of 12 weeks.
4	Usual Care : A daily multivitamin plus standard care monitoring.

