1.3 Calcitriol and Bone Health

Calcitriol could prove to be a safe, low-cost treatment for preserving bone health in breast cancer patients. Human beings obtain Vitamin D from sunlight, food, and supplementation.²⁶ Vitamin D plays a vital role in maintaining proper bone health and works in conjunction with calcium. Higher levels of vitamin D have been shown to increase the intestinal absorption of calcium.²⁷ One study demonstrated that an increase in serum vitamin D produced a 45%-65% increase in intestinal absorption of calcium.²⁸ Although no consensus exists on optimal vitamin D levels, most experts agree a 25-hydroxyvitamin D level of less than 20 ng per milliliter is deficient.²⁹ Based on this level, it is estimated more than 1 billion people worldwide and between 40%-100% of elderly U.S. residents are vitamin D deficient.³⁰⁻³³ More than 50% of postmenopausal women already under treatment for osteoporosis have deficient vitamin D levels.^{34, 35}

Bone health is a major concern in women undergoing treatment and who have completed treatment for breast cancer. Cancer-treatment-induced bone loss (CTIBL) is a long-term side-effect of various breast cancer treatments.³⁶ Chemotherapy, hormone therapy, and irradiation frequently lead, either directly or indirectly, to bone mass depletion in breast cancer patients.³⁷ Studies have documented accelerated bone loss in breast cancer patients, and this bone loss frequently goes undiagnosed.³⁸⁻⁴⁰ Breast cancer survivors have greater bone loss than women of similar age who were not diagnosed with cancer.⁴¹⁻⁴³ Risk factors for bone loss are already present in many women prior to a breast cancer diagnosis.⁴⁴ Treating bone loss in a prophylactic manner leads to greater success than delayed treatment.^{45, 46} The Women's Health Initiative (WHI) and other

studies have found that postmenopausal breast cancer survivors had increased risk of fractures.⁴⁷⁻⁴⁹

[figure not shown]

Fig. 2. Extent of bone loss due to cancer therapy. Menopausal women lose bone at a rate of 1% to 2% yearly. Cancer treatments, such as aromatase inhibitor therapy and chemotherapy, accelerate this process, leading to significant bone loss and subsequent skeletal complications (39, 75-79). Adapted from Skeletal Complications Across the Cancer Continuum CME Lecture 2005 series with permission from the Postgraduate Institute for Medicine.

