3.2 Women of child-bearing potential (i.e. women who are pre-menopausal or not

surgically sterile) must use acceptable contraceptive methods (abstinence, intrauterine device (IUD), or double barrier device) and must have a negative serum or urine pregnancy test within 1 week prior to beginning treatment on this trial. Contraceptive use needs to be continued at least 1 month after the trial has ended.

- 3.3 Must provide informed consent.
- 3.4 Must be willing to discontinue use of calcium and/or vitamin D supplements.
- 3.5 Participants must have an ionized serum calcium level within normal limits (1.19-1.29mmol/L) and a total corrected serum calcium of < 10.2mg/dl.
- 3.6 Must have a functional capacity rating of ≤ 2 on the Eastern Cooperative Oncology Group (ECOG) performance status when assessed at baseline.¹⁵⁴
- 3.7 Must have the approval of their treating physician (or physician's nurse practitioner or physician's assistant) to participate in sub-maximal physiological fitness testing and a low to moderate home-based walking and progressive resistance exercise program and to receive the 12-week supplementation of calcitriol 45 μ g. Participants assigned to either of the calcitriol treatment arms will be instructed to stop taking calcium and/or vitamin D supplements.
- 3.8 Must be less than five years from the diagnosis of breast cancer and have received chemotherapy, radiation therapy, and/or hormonal therapy. Chemotherapy and radiation therapy, if received, must have been completed prior to study enrollment. Hormonal therapy may be ongoing.

Exclusion Criteria:

- 3.9 Subjects with life-threatening conditions that would preclude them from breast cancer treatment including chronic cardiac failure, which is unstable despite medication use, uncontrolled hypertension, uncontrolled diabetes mellitus, or unstable coronary artery disease.
- 3.10 Patients who had a myocardial infarction within the past year.
- 3.11 Patients with severe metabolic disorders, which includes phenylketonuria (PKU), homocystinuria, and Fabry's disease, that would preclude them from taking calcitriol.
- 3.12 Patients with impaired renal function (CRCL < 60 mL/min) or who had kidney stones (calcium salt) within the past 5 years.
- 3.13 Patients with hypercalcemia (corrected serum Ca > 10.2 mg/dl) or a history of

hypercalcemia or vitamin D toxicity.

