7.0 Statistical Considerations

7.0 Primary measures and analyses:

- 7.0.1 Bone Resorption: NTX
- 7.0.2 Bone Formation: BAP

Since the primary objective of this pilot study is to gather preliminary efficacy and feasibility data for the development of a planned career development grant application, the primary analyses will consist of calculating mean change scores (i.e., baseline assessment minus final assessment) and standard deviations for the two variables above. In addition, a paired-sample t-test will be used to calculate the differences between the baseline and end of trial value for both BAP and NTX. An independent t-test will be used to calculate the difference between the baseline and end of trial value for both BAP and NTx between the trial arms. Lastly, ANCOVA models will be used for BAP and NTx with the addition of relevant covariates collected during the study. Results of these two analyses will be interpreted cautiously because of the limited sample size.

7.1 Secondary measures and analyses:

- 7.1.1 Physical Activity: ACLS and Pedometer
- 7.1.2 Aerobic Capacity: VO2max Treadmill Test
- 7.1.3 Muscular Fitness: Handgrip Dynamometer and 7-10 Repetition Maximum
- 7.1.4 Muscle Mass: Bioelectrical Impedance Analysis
- 7.1.5 Since the secondary aims relating to physical activity, aerobic capacity, muscular fitness, and muscle mass, respectively, are intended to gather preliminary efficacy data for the development of a planned K07 submission, the secondary analyses will consist of calculating mean change scores (e.g., baseline assessment subtracted from the final assessment, and baseline subtracted from the follow-up assessment), standard deviations, and correlations on these variables for the two study arms. Additional exploratory analyses will use mixed effects models, to compare mean bone health within the four treatment arms during the intervention time and follow-up period of the study. The mixed effects

[figure not shown]

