models will use the change in bone health levels (NTx, BAP) during the study and during follow-up as the outcomes. The subject will be included as a random effect, and treatment arms, time, their interactions, hormone therapy, and baseline bone health levels will be included as fixed effects. Individual trial arms will be compared to each other and the interaction term between treatment and time is used to investigate whether the benefit of the intervention changes with time. **Because of the small sample size and the resulting low statistical power, these secondary analyses will be interpreted very cautiously and only used to aid in the design of a study for our future K07 application.**

7.1.6 Additional analyses will examine between group differences in the other outcome measures. These will include Physical Activity (ACLS and Pedometer), aerobic capacity (VO₂max treadmill test), muscular strength (handgrip dynamometry and 7-10 repetition maximum), and muscle mass (Bioelectrical Impedance).

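### Randomisation is blocked for arm size but not stratified on ongoing hormonal therapy, the one clinical covariate the plan names for NTx/BAP change, and the primary arm comparisons do not commit to adjusting for it

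*Combined protocol and SAP*

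**What the plan says.** On allocation, section 4.1.1 reads: "This study will use a block-randomized scheme with block sizes of 8 to ensure an equal distribution among the four arms". Sections 4.1.2 and 7.2.1 plan 72 women, 18 per arm. No stratification factor is named.

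On hormonal therapy, criterion 3.8 requires any chemotherapy and radiation to be finished before enrolment, but adds: "Hormonal therapy may be ongoing". Of these three treatments it is therefore the only one that can still be active during the 12 weeks. Section 1.3 gives the reason to care about it: "Chemotherapy, hormone therapy, and irradiation frequently lead, either directly or indirectly, to bone mass depletion in breast cancer patients".

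On analysis, section 7.0 lists for the two primary markers paired t-tests, a between-arm test ("An independent t-test will be used to calculate the difference between the baseline and end of trial value for both BAP and NTx", compared between arms) and ANCOVA models whose covariates are described only as relevant ones, with none named. Section 7.1.5 then describes an exploratory mixed model of NTx/BAP change in which "treatment arms, time, their interactions, hormone therapy, and baseline bone health levels will be included as fixed effects". Hormone therapy is the only clinical characteristic on that list.

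By 4.1 and 5.3.1, randomisation follows the baseline assessments, and the clinical and medication forms are among the initial assessments. A woman's therapy status is therefore known before she is allocated.

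**The concern.** The plan treats hormone therapy as important enough to be a fixed effect in its exploratory model of the primary markers, yet it neither balances the arms on it nor commits to adjusting for it in the analyses called primary. With 18 women per arm, blocking on arm size leaves the mix of users and non-users to chance.

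If therapy status is related to the 12-week change in NTx or BAP, an uneven mix moves an unadjusted arm contrast up or down for a reason unrelated to calcitriol or exercise. The product of this pilot is a set of mean changes and SDs to carry into a grant application. Noise from a factor known at entry would be carried forward with them.

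**Working it through.** **Inputs.** From the documents: four arms, blocks of 8, 72 women (4.1.1, 4.1.2, 7.2.1). Section 1.6 still says 54; 72 is used here because it appears in both the allocation and sample-size sections. Not in the documents, so assumed: the share of users p, taken from 20% to 80%, and the user/non-user difference in 12-week marker change, δ, taken as 0.5 to 1.0 SD.

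**1. The plan's own figure.** 72/8 = 9 full blocks with 8/4 = 2 women per arm in each, so 9 × 2 = 18 per arm. The stated equal distribution is reproduced. It concerns arm size only.

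**2. Imbalance without stratification.** Users per arm are independent Binomial(18, p). The difference in share between two arms has SD √(2p(1−p)/18), for example √(2 × 0.25/18) = 16.7 points at p = 0.5. Results are symmetric in p and 1−p. The one-pair column is exact; the last column uses 200,000 simulations.

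| Share of users | SD of difference, one pair | Given pair differs by ≥ 4 women | At least two of four arms differ by ≥ 4 |
|---|---|---|---|
| 20% or 80% | 13.3 points | 14% | 45% |
| 30% or 70% | 15.3 points | 20% | 57-58% |
| 40% or 60% | 16.3 points | 23% | 63% |
| 50% | 16.7 points | 24% | 65% |

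Four women of 18 is 4/18 = 22 points. With the total number of users held fixed instead, the last column is 65% (36 users of 72) and 59% (50 users).

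**3. Effect on a contrast.** Shift = δ × 4/18. For δ = 0.5 SD this is 0.11 SD; for δ = 1.0 SD it is 0.22 SD. The standard error of a difference between two arms of 18 is √(1/18 + 1/18) = 0.33 SD. A 4-woman gap therefore moves the contrast by one third to two thirds of a standard error.

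**4. With stratified blocks.** Two strata (on/off therapy) were simulated 20,000 times at user shares of 50% and 70%. A gap between any two arms equivalent to 3 or more of 18 women has probability 84% and about 80% without stratification, and did not occur with it. The mean gap between the highest and lowest arm falls from 22-24 points to 3.0-3.4 points with blocks of 4, or 4.5-4.9 points with blocks of 8.

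**5. Cost in arm size.** An incomplete last block can leave arms unequal by up to 1 woman per stratum (blocks of 4) or 2 (blocks of 8). Over two strata, that is up to 2 or 4 women.

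**The case against.** The strongest objection is that the documents do not show that hormonal therapy affects the outcome analysed. Section 1.3 speaks of loss of bone mass, and its figure caption says "Cancer treatments, such as aromatase inhibitor therapy and chemotherapy, accelerate this process". Neither addresses 12-week change in NTx or BAP. The outcome is change from baseline, so a stable difference in marker level between users and non-users cancels; only a difference in change matters. This stands. The values of δ above are assumptions, and the shift in SD units depends on them.

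Second, the primary analyses already include an ANCOVA, and hormone therapy could enter it as a relevant covariate. That is fair, and naming it there would be an alternative to stratifying. As written, however, nothing commits to it, and the t-tests remain unadjusted.

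Third, this is a pilot, section 7.0 promises cautious interpretation, and full blocks give exactly equal arms. Caution does not remove noise from the estimates, but this does limit how much weight the point can bear.

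Four stronger readings are tempting and unsupported:

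- A reader might infer that a sizeable imbalance is likely in any given comparison. It is not (14-24%). The 45-65% figure is for the most extreme of six pairs, and it drops below one half at shares near 20% or 80%.
- A reader might infer bias. Chance imbalance under randomisation is already part of the unadjusted test's error, and the comparison remains valid.
- A reader might infer that aromatase inhibitor use is the factor the plan singles out. The caption mentions it beside chemotherapy, and the covariate in 7.1.5 is hormone therapy.
- A reader might infer that 7.1.5 wrongly lumps drug types together. It does not say how the term is coded.

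**Conclusion.** The point holds as a modest design and analysis gap. The plan names one clinical covariate for its marker model, knows its value before allocation, and uses it neither in the randomisation nor, by commitment, in the primary between-arm comparisons. The consequence is avoidable noise, smaller than the sampling error of a contrast even at the upper end of the assumed effect. It does not undermine the randomised comparison.

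The imbalance probabilities rest only on the assumed share of users. The size of the shift rests on an effect on 12-week change that the documents do not establish; if there is none, balancing gains little. Exclusion criteria 3.18 and 3.19 are redacted, so any bearing they have on therapy status cannot be checked. The change is worth making because it is cheap.

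**What to change.** In 4.1.1, stratify the permuted blocks by ongoing hormonal therapy at entry (yes/no), preferably with blocks of 4 within each stratum. In 7.0, make the between-arm comparison of NTx and BAP an ANCOVA that includes arm, this stratum and the baseline marker. The two changes belong together, because an unadjusted t-test after stratified allocation does not use the balance gained. The model has six parameters (intercept, three arm terms, stratum, baseline), leaving 72 − 6 = 66 residual degrees of freedom with complete data.

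If allocation can no longer be changed, naming hormonal therapy and the baseline marker in the primary ANCOVA is the part to keep. Coding aromatase inhibitors separately from other agents is optional and should be labelled exploratory.

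The cost is a second randomisation list, one model term, and the loss of exactly 18 per arm: totals may differ by up to 2 women with blocks of 4, or up to 4 if blocks of 8 are kept.

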5.0 Treatment Protocol

- 5.1 This will be a four-arm clinical trial of an intervention examining the feasibility and efficacy of calcitriol 45 µg alone, a structured home-based walking/progressive resistance exercise program alone, along with the combination of calcitriol 45 µg and a structured home-based walking/progressive resistance exercise program for the maintenance of proper bone health among invasive breast cancer survivors.
- 5.2 Potentially eligible subjects at Strong Memorial Hospital will be approached by their physician either at a regularly scheduled oncology appointment or by standardized letter in the mail. The initial contact will assess whether the patient has any interest in participating in a clinical trial to preserve bone health. If interested, patients will be invited to call or come to our research center for screening to determine their eligibility for the study. If the patient is eligible, study personnel will explain the details of the study and obtain informed consent from patients who agree to participate.

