5.3 Consent Process and Initial Assessments

- 5.3.1 Cancer survivors less than 5 years removed from the diagnosis of breast cancer who meet the eligibility criteria including approval from their physician will be invited to participate in the trial.

Upon consent, with help from the study coordinator, the patient will complete an On-Study Data Form, a Clinical Record Form, and a Medication Form, providing clinical and demographic data. Questions concerning the patient's sun exposure history, medical history, supplement usage history, exercise history, and baseline brief symptom inventory are also included. The study coordinator will obtain information necessary to complete these three forms from the patient's medical records when the patient is unable to provide this information in sufficient detail (e.g., staging, Karnofsky Performance Scale, surgical procedures, types and doses of treatments). Additionally, patients will be evaluated on vitals (Resting Heart Rate, Height, Weight & Blood Pressure), aerobic capacity (VO₂max Treadmill Test and Resting Metabolic Rate (RMR) test) muscular strength (Handgrip Dynamometry and 7-10 repetition maximum test), skeletal muscle mass (Bioelectrical Impedance Analysis), and physical activity. (Note: Baseline measures of physical activity involve fitting each participant with a Pedometer for a 5-day baseline assessment). Patients will also provide a blood sample at this time.

- 5.3.2 Patients will be randomized to one of four treatment arms. Study medication and instructions for calcitriol 45 µg will be given and reviewed with all patients. Arm 2 and arm 3 patients will also receive instructions and an Exercise Kit for the home-based walking and progressive

resistance exercise program.

5.3.2.1 Patients assigned to Treatment Arm 1 will receive a 12-week supply of calcitriol, which consists of twelve 45 μ g pills of calcitriol to be taken once a week (QW).

5.3.2.2 Patients assigned to Treatment Arm 2 will receive a 12-week supply of daily multivitamins and a home-based walking and progressive resistance exercise regimen to follow for a total duration of 12 weeks.

5.3.2.3 Patients assigned to Treatment Arm 3 will receive a 12-week supply of calcitriol, which consists of twelve 45 μ g pills of calcitriol to be taken once a week (QW) and a home-based walking and progressive resistance exercise regimen to follow for a total duration of 12 weeks.

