5.3.2.4 Patients assigned to Treatment Arm 4 will receive a 12-week supply of daily multivitamins but will not receive an exercise regimen to follow during the study period.

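### A fixed, printed block size of 8, with no concealment described, lets a fully informed observer know at most 14% of assignments; undisclosed varying blocks are a cheap improvement

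*Combined protocol and SAP*

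**What the plan says.** Section 4.1.1 gives the scheme: "This study will use a block-randomized scheme with block sizes of 8 to ensure an equal distribution among the four arms". Section 4.1.2 gives the target: "A total enrollment of 72 patients is planned (18 in each treatment arm". On how the list is produced, section 4.1 says only: "Randomization will be determined by means of a computer-generated random number table". No list holder, central release, sealed system or stratification is described.

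On timing, section 4.1 places randomization after eligibility, consent, physician consent and baseline; women who "complete baseline assessments will immediately be randomized to one of four treatment arms". Under section 5.3.1, baseline includes "fitting each participant with a Pedometer for a 5-day baseline assessment".

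The documents use neither open-label nor single-site, but both are fair inferences. Section 5.2 names one recruiting hospital: "Potentially eligible subjects at Strong Memorial Hospital will be approached by their physician". The arms are visibly different (a weekly capsule, an exercise kit, or a daily multivitamin), and no placebo or blinding is described. Section 5.3.2.4, for example, says: "Patients assigned to Treatment Arm 4 will receive a 12-week supply of daily multivitamins but will not receive an exercise regimen to follow".

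The study coordinator has a part on both sides of randomization. Before it, section 5.3.1 says: "Upon consent, with help from the study coordinator, the patient will complete an On-Study Data Form". After it, sections 5.5.1.3 and 5.6.2.3 have the coordinator making the calcitriol reminder calls and answering questions about the exercise program.

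**The concern.** With four arms and a block of 8, each block holds two places per arm. Once seven places are filled and known, the eighth is determined, and the seventh sometimes is too. Earlier in the block, an arm whose two places are used cannot come next. Printing the block size gives anyone with the protocol the first thing needed to work this out. In an unblinded trial at one site, the coordinator's duties could supply the second, which is the run of past assignments.

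Foreknowledge could influence whom to approach, when to consent or schedule a woman, or in what order women are randomized. Fitter women might, for example, be steered toward exercise. Laboratory measurement of NTx and BAP does not protect against this, because selection changes who is in each arm rather than how the marker is read. With 18 per arm, two steered women are 2/18 = 11% of an arm, and section 7.0 plans between-arm t-tests and ANCOVA on those arms.

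**Working it through.** **The plan's own figures.** 72/8 = 9 complete blocks, and 9 × 2 = 18 per arm. Sections 4.1.1 and 4.1.2 agree. The documents give no predictability figure; those below are derived.

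**Observer assumed.** Knows the block size, where blocks start and every earlier assignment in order.

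**Certain assignments, fixed block of 8.**
- Position 8 is always known: 1 per block.
- Position 7 is known only if the last two places are the same arm: 4 × (2/8) × (1/7) = 1/7.
- Position 6 or earlier is never known, since three remaining places cannot all be one arm.
- Share: (1 + 1/7)/8 = 8/56 = 14.3%. Over 72 women: 9 + 9/7 = 10.3.

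**At least one arm ruled out.** After j assignments no arm is used up with probability C(4,j)·2^j / C(8,j): 1, 1, 6/7, 4/7 and 8/35 for j = 0 to 4, and 0 after that. The sum is 3.657, so the excluded share is (8 − 3.657)/8 = 54.3%.

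**Best guess.** Guess the arm with most places left. The expected success rates at positions 1 to 8 are 0.250, 0.286, 0.333, 0.400, 0.443, 0.476, 0.571 and 1. They sum to 3.760, and 3.760/8 = 47.0%, against 25% by chance.

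**At consent rather than at randomization.** If one earlier woman still awaits randomization, position 8 is known only when positions 7 and 8 are the same arm: (1/7)/8 = 1.8%. With two or more ahead, nothing is certain. Inputs:
- Accrual: section 7.2.2 gives about ten months for 72 women, so 10 × 30.4/72 = 4.2 days per woman.
- Lag: 5 days, from the pedometer period (assumed to be the whole lag).
- Arrivals: Poisson (assumed).

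The mean number ahead is 5/4.22 = 1.18, so P(0) = 0.306 and P(1) = 0.362. The certain share is 0.306 × 14.3% + 0.362 × 1.8% = 5.0%, or 3.6 of 72 women. A longer lag lowers it: the same formula gives 3.3% at 7 days and 1.7% at 10 days.

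**Varying the block size.** These figures are from simulation with an observer who updates optimally. The second row is the list proposed below, with its composition known to the observer; the next two draw sizes independently from a known menu.

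| Scheme | Certain | Arm ruled out | Best guess |
|---|---|---|---|
| Fixed 8 (exact) | 14.3% | 54% | 47% |
| Two each of 8, 12, 16, random order | about 4% | about 19% | about 44% |
| Independent draws from 8/12/16 | 2.3% | not computed | 43% |
| Independent draws from 4/8 | 7.3% | not computed | 48% |

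The 2.3% belongs to independent draws, which need not end at exactly 72. The proposed list does (2 × 8 + 2 × 12 + 2 × 16 = 72), at the price of being somewhat more predictable if its composition leaks. A disclosed 4/8 mix would not lower the guess rate at all.

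**The case against.** The strongest reply is that 14.3% is a ceiling. It needs an observer who tracks every assignment, knows the block boundaries and has no unrandomized woman ahead. The documents do not say who holds the list or sees the running sequence. This stands, and 14.3% should not be read as what staff will know. Steering before consent is also exposed to the baseline lag, where about 5% is the more relevant figure. The ceiling applies only when randomization is triggered.

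A reader might infer that the same people screen, consent and schedule baseline. The documents do not show this. Section 5.2 has the woman's physician make the first approach, in clinic or by letter, and unspecified study personnel obtain consent. No section says who schedules baseline. Section 3.7 also requires the treating physician's approval for both interventions, whatever the arm. What is documented is narrower: the coordinator helps with baseline forms and later makes arm-specific contacts.

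Randomizing after baseline is already in section 4.1, which is a real safeguard, though not against choosing whom to approach or in what order. Finally, the trial is a pilot whose results are to be interpreted cautiously, and no estimate of bias in NTx or BAP is available. That limits the severity.

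**Conclusion.** The point holds as a minor, cheap improvement. For a fully informed observer, certain knowledge runs from about 5% at consent (5-day lag, Poisson accrual) to a maximum of 14.3% at randomization. The 54% and 47% figures are upper bounds under the same full-information assumption.

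Two stronger readings should be resisted. One is that recruiting staff will in fact foresee 14% of assignments; the documents do not establish that anyone has the necessary information. The other is that varying the block size largely removes predictability. It sharply cuts certain knowledge and arm exclusion, but leaves the best-guess rate almost where it was, at about 44% against 47%. The absence of a described concealment step therefore matters at least as much as the block size.

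**What to change.** - Replace the single size with permuted blocks of randomly varying size in multiples of 4. Two each of 8, 12 and 16 in random order total 72 and keep 18 per arm.
- Take the sizes out of the protocol text available to enrolling staff and put them in a restricted randomization document. No assignment is then strictly certain within the list; only at its very end does the printed 18 per arm give the last place away.
- State that someone not involved in enrolment holds the list and releases each assignment only once the baseline assessments that section 4.1 already requires are recorded.

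The cost is a new list, a named list holder and a sentence or two of protocol text, with slightly more possible imbalance between arms part-way through accrual. The example assumes the 72 women of sections 4.1.2 and 7.2.1. Section 1.6 gives 54, which is 6.75 blocks of 8, so the total should be reconciled before the list is drawn.
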